8.	
Subjects with symptomatic heart failure, as defined by the following New York Heart Association functional classes:
 
 • Class III – Patients with cardiac disease resulting in marked limitation of physical activity. They are comfortable at rest. Less than ordinary activity causes fatigue, palpitation, or dyspnea. • Class IV – Patients with cardiac disease resulting in inability to carry on any physical activity without discomfort. Symptoms are present even at rest or minimal exertion. If any physical activity is undertaken, discomfort is increased.
9.	
Subjects with a history of atrial fibrillation or chronic thrombosis requiring treatment with anticoagulants, eg, warfarin, rivaroxaban (see Table 6).

10.	
Subject with a recent history (<6 months) of clinically significant orthostatic hypotension or falls.

11.	
Subjects who answer “yes” on the C-SSRS Suicidal Ideation Item 4 or Item 5 (Active Suicidal Ideation with Some Intent to Act, Without Specific Plan, or Active Suicidal Ideation with Specific Plan and Intent) and whose most recent episode meeting the criteria for C-SSRS Item 4 or Item 5 occurred within the last 6 months, OR
 
Subjects who answer “yes” on any of the 5 C-SSRS Suicidal Behavior Items (actual attempt, interrupted attempt, aborted attempt, preparatory acts, or behavior) and whose most recent episode meeting the criteria for any of these 5 C-SSRS Suicidal Behavior Items occurred within the last 2 years, OR
 
Subjects who, in the opinion of the investigator, present a serious risk of suicide.

12.	
Subjects with substance abuse or dependence disorder, including alcohol, benzodiazepines, and opioids, but excluding nicotine, within 6 months prior to signing the ICF.

13.	
Subjects with any condition or surgery that could possibly affect drug absorption, including, but not limited to complicated appendectomy or cholecystectomy, bowel resections, bariatric weight loss surgery, gastric banding, or gastrectomy.

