14.	
Subjects with a history of malignancy other than the following:
 
 • Non-metastatic basal or squamous cell carcinoma of the skin or carcinoma in situ that was surgically removed in total >1 year before signing the ICF and had not recurred • Another type of malignancy that had been in remission for ≥5 years before signing the ICF and had not recurred • Subjects with history of localized malignancy that was surgically removed and has been in remission for <5 years may be eligible for the trial only with explicit approval by the medical monitor

Prior or Concomitant Medications
	
15.	
Subjects with a positive urine drug screen or a positive test for alcohol are excluded (note: individuals who test positive for alcohol may be rescreened). Subjects with a positive urine drug screen resulting from use of marijuana (any THC-containing product), prescription, or over-the-counter medications or products that, in the investigator’s documented opinion, do not signal a clinical condition that would impact the safety of the subject or interpretation of the trial results may continue evaluation for the trial following consultation and approval by the medical monitor.

16.	
Subjects who are using prohibited medications prior to randomization (as listed in Table 5) or who would be likely to require prohibited concomitant therapy (as listed in Table 6) during the trial.

Physical Examination and Clinical Laboratory Results	
17.	
Subject with clinically significant orthostatic hypotension at screening associated with either of the following:
 
 • Loss of consciousness (eg, syncope) • Presyncope (eg, severe dizziness/lightheadedness) requiring stabilization to avoid fall
18.	
 • Subjects with a supine/sitting blood pressure ≥ 160 mmHg (systolic) or ≥ 100 mmHg (diastolic). The average of 2 supine/sitting measurements will be used to assess eligibility. • For subjects with a supine/sitting blood pressure ≥ 140 mmHg (systolic) or ≥ 90 mmHg (diastolic), approval is required by medical monitor on a case-by-case basis. • Subjects receiving >2 antihypertensive medications for blood pressure control.

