8.3.2 Vital Sign Measurements

Vital signs include systolic and diastolic blood pressures, heart rate, and body temperature. Duplicate blood pressure and heart rate measurements will be obtained sitting/supine (after 5 minutes of rest) followed by a single standing measurement (after 2 minutes of rising from sitting/supine position). The duplicate values will be individually recorded, and the values will be averaged by the sponsor for the time point assessment. At each visit, body temperature will be obtained once, at the time of the first blood pressure measurement.

Any clinically relevant changes occurring during the trial will be recorded in the AE section of the eCRF.

Further details on taking vital sign measurements are provided in the appropriate trial specific manuals.

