9.3. Vital Sign Measurements

Vital signs will include systolic and diastolic blood pressures, heart rate, and body temperature. Duplicate blood pressure and heart rate measurements will be obtained sitting/supine (after 5 minutes of rest) followed by a single standing measurement (after 2 minutes of rising from sitting/supine position). The duplicate values (sitting/supine) will be individually recorded, and the values will be averaged by the sponsor for the time point assessment. At each visit, body temperature will be obtained once, at the time of the first blood pressure measurement. Orthostatic blood pressure parameters are calculated as the average measurement in the sitting/supine position minus the measurement in the standing position for the corresponding parameters, for each visit.

Potential clinically significant values and changes of vital signs parameters are:

- Weight: weight gain or loss >7% from baseline
- Systolic blood pressure (sitting/supine average)
 - Max observed value >160 mmHg
 - Max increase from baseline >20 mmHg
 - Min observed value <90 mmHg
 - Greatest decrease from baseline >20 mmHg
- Orthostatic Systolic Blood Pressure
 - Greatest decrease upon standing compared with sitting/supine position ≥ 20 mmHg
 - Max increase upon standing compared with sitting/supine position ≥ 20 mmHg
- Diastolic blood pressure (sitting/supine average)
 - Max observed value >100 mmHg
 - Max increase from baseline >10 mmHg
 - Min observed value <50 mmHg
 - Greatest decrease from baseline <10 mmHg
- Orthostatic Diastolic Blood Pressure

- Greatest decrease upon standing compared with sitting/supine position ≥ 10 mmHg
- Max increase upon standing compared with sitting/supine position ≥ 10 mmHg
- Heart Rate (sitting/supine average)
 - Max observed value > 120 bpm
 - Min observed value < 50 bpm

Vital signs data including changes from baseline will be summarized through descriptive statistics by visit and treatment group. Potential clinically significant values and changes defined above will be summarized based on the maximum/minimum actual post-baseline values and maximum increase/greatest decrease from baseline. Additionally, all relevant data will be listed for the FAS.

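### SAP 9.3 counts orthostatic and heart-rate findings on the worst post-baseline value without regard to baseline status, so new and pre-existing cases cannot be told apart in the table

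*SAP*

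**What the plan says.** SAP 9.3 computes the orthostatic parameters within each visit: "Orthostatic blood pressure parameters are calculated as the average measurement in the sitting/supine position minus the measurement in the standing position". The orthostatic rows are worded in the same way, for example "Greatest decrease upon standing compared with sitting/supine position", with thresholds of 20 mmHg systolic and 10 mmHg diastolic, and corresponding rows for a rise. The heart-rate rows are fixed limits, above 120 and below 50 bpm. The table rule is: "Potential clinically significant values and changes defined above will be summarized based on the maximum/minimum actual post-baseline values and maximum increase/greatest decrease from baseline".

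In the same list, weight and resting systolic and diastolic pressure have criteria tied to baseline, such as "Max increase from baseline >20 mmHg" for systolic pressure. The orthostatic and heart-rate rows have none.

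The section also plans this: "Vital signs data including changes from baseline will be summarized through descriptive statistics by visit and treatment group". Individual data are listed for the full analysis set.

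On eligibility, Protocol 5.2 exclusion 10 covers a recent history (under 6 months) of "clinically significant orthostatic hypotension or falls". Exclusion 17 begins "Subject with clinically significant orthostatic hypotension at screening associated with either of the following" and then names loss of consciousness, and presyncope that needs stabilization. Exclusion 23 covers other abnormal vital signs unless the investigator judges them not medically significant. None of the three sets a mmHg limit on the standing drop.

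**The concern.** A subject who drops 25 mmHg on standing before the first dose, without symptoms, may be randomized. If the drop recurs at any later visit, that subject appears in the count exactly as one whose drop began on drug. The reader of the table cannot tell which is which.

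Vital-sign changes are part of the primary safety endpoint, in a population aged 50 to 85 that includes dementia with Lewy bodies. A count that carries baseline prevalence in every arm makes a real effect on standing pressure harder to see. With small arms it can also show a difference that was there before dosing. The same gap applies to the heart-rate rows.

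**Working it through.** The plan states no figure on this point, so the main check is textual. The arithmetic only shows what size the effect could have.

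**1. Does baseline enter the rows?** The comparator in each orthostatic row is body position at the same visit. In the table rule, the part about change from baseline fits only rows written as such a change (weight, resting pressures). The orthostatic and heart-rate rows therefore fall under the worst post-baseline value. SAP 4.4.4 lets unscheduled readings enter the worst case, which adds chances to be counted.

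**2. What do the other safety domains get?**

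| Domain | Reference to baseline in the categorical tables |
|---|---|
| Laboratory (SAP 9.2.1, 9.2.2) | Shift from baseline to worst on-treatment category |
| ECG (SAP 9.5) | Normal/abnormal shift; QTcF increase from baseline |
| Weight, resting blood pressure (SAP 9.3) | Change-from-baseline criteria |
| Orthostatic pressure, heart rate (SAP 9.3) | None |

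**3. Are the data there?** Vital signs, including a standing reading, are scheduled at Screening, Baseline and Weeks 1, 3, 6, 12 and 14 (Protocol Table 1 and 8.3.2). That gives a baseline value, as defined in SAP 4.4.6, and five scheduled post-baseline readings.

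**4. How often would a pre-existing case be counted?** Let q be the chance that a pre-existing drop recurs at a visit (assumption; visits independent). P(counted) = 1 − (1 − q)^5. For q = 0.3, 0.5 and 0.8 this gives 0.83, 0.97 and more than 0.99. A pre-existing case is very likely to be counted.

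**5. Dilution.** Let p be the share enrolled with a baseline drop (assumption), f = 1 − 0.5^5 = 0.969, and new onset among the others 20% on active and 5% on placebo (assumption). The counted rates are pf + (1 − p) × 0.20 and pf + (1 − p) × 0.05.

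| p | Active | Placebo | Difference (points) | Ratio |
|---|---|---|---|---|
| 0 | 0.200 | 0.050 | 15.0 | 4.00 |
| 0.1 | 0.277 | 0.142 | 13.5 | 1.95 |
| 0.2 | 0.354 | 0.234 | 12.0 | 1.51 |
| 0.3 | 0.431 | 0.326 | 10.5 | 1.32 |

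**6. Chance imbalance before dosing.** Pre-existing cases in two arms are taken as independent binomials (n, p), with every baseline case recurring.

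| n per arm | Difference | p = 0.1 | p = 0.2 | p = 0.3 |
|---|---|---|---|---|
| 20 | ≥2 | 0.42 | 0.55 | 0.60 |
| 20 | ≥3 | 0.18 | 0.32 | 0.39 |
| 10 | ≥2 | 0.24 | 0.39 | 0.46 |
| 10 | ≥3 | 0.06 | 0.16 | 0.22 |

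The row of 20 per arm corresponds to the 60-subject minimum. The row of 10 per arm is an assumption, included because enrollment closed early without the planned size being reached (SAP 1 and 15).

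**The case against.** **Baseline is not absent from SAP 9.3.** By-visit statistics include change from baseline and may cover the orthostatic parameters. Listings allow a check subject by subject, and the table shells are in a separate document not available here. This stands: the gap is in the planned count. But group means and listings do not give the number of new cases.

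**A reader might infer that the table reports on-treatment events, or contaminates the adverse event of special interest (AESI).** The documents do not support that. SAP 9.3 calls these rows potentially significant values and changes, after baseline. The AESI is defined by symptoms and summarized through TEAEs, which must develop, worsen or become serious during treatment (SAP 9.1 and 9.1.6).

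**A reader might infer that every asymptomatic drop is eligible.** It may be, at the investigator's discretion under exclusion 23. Exclusion 10 also removes subjects with recent falls.

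**A reader might extend the point to the resting pressure limits.** Those sit beside change-from-baseline rows, so only heart rate shares the gap.

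**A reader might infer that loose wording on sitting or supine rest makes the drop unreliable within a subject.** Protocol 8.3.2 refers to trial manuals that are not available here and may settle this. With enrollment closed, a protocol change would also come late. It is not part of this point.

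**Counting everyone at the worst value is a defensible, sensitive screen.** That is right. Restricting the count to subjects without a baseline drop would hide worsening, for example from 20 to 45 mmHg.

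**Conclusion.** The point holds as a cheap improvement to the SAP. The orthostatic and heart-rate rows carry no reference to the subject's baseline status and have no shift table, unlike laboratory and ECG data. The count can therefore mix pre-existing with new cases. The consequences are inflated rates in all arms, a diluted contrast and chance imbalance in small arms. A directional bias cannot be inferred, because randomization balances pre-existing cases in expectation.

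The textual finding needs no assumption. The sizes rest on assumed prevalence (10% to 30%), recurrence and new-onset rates, none of which the documents give. The imbalance figures also depend on the cut-off: moving it from two subjects to three lowers them to 0.18 to 0.39 with 20 per arm. They are illustrations. The analysis is descriptive, with no between-arm test planned for these rows.

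**What to change.** In SAP 9.3, keep the all-subject count and add a table of baseline category by worst post-baseline category, by treatment group, for the orthostatic parameters and heart rate.

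- Grade the orthostatic categories so that worsening in subjects already positive at baseline stays visible: for example a systolic drop of <20, 20 to <30 and ≥30 mmHg, with matching diastolic bands starting from 10 mmHg. Alternatively, pair a two-level shift with the change from baseline in the standing drop.
- For heart rate, use the limits already in the list (<50, 50 to 120, >120 bpm).
- Use the safety baseline of SAP 4.4.6.

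The cost is a short paragraph and one extra table. No new data are needed, and the planned count loses nothing.

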9.4. Physical and Neurological Examination

A full physical examination will consist of measurement of height (screening only) and weight and a review of the following body systems: head, ears, eyes, nose, mouth, skin, heart and lung examinations, lymph nodes, gastrointestinal, and musculoskeletal systems.

A full neurological examination will include an assessment of the subject's mental status (level of consciousness, orientation, speech, memory, etc), cranial nerves, motor (muscle appearance, tone, strength and reflexes), sensation (including Romberg sign), coordination, and gait.

Results (normal, abnormal, or not done) from the assessment will be reported. All deviations from normal will be recorded, including those attributable to the patient's disease.

Any condition present at the on-treatment and post-treatment physical and neurological examinations that was not present at the baseline examination will be documented as an AE.

Physical and neurological examination will be presented as a listing of abnormal physical and neurological examination. Medical history will be presented in a separate listing.

9.5. Electrocardiogram

At Screening, a triplicate set of 12-lead electrocardiograms (ECGs) will be obtained to assess subject eligibility. Based on the QT interval as corrected for heart rate by Fridericia's formula (QTcF), a subject will be excluded if the average QTcF interval of the triplicate set of screening ECGs is ≥ 450 msec, as read by the central ECG service.

At all other time points (Baseline, Weeks 1, 3, 6, 12, and 14) a single ECG will be performed and evaluated at the investigational site to monitor safety during the trial. Any clinically relevant changes occurring during the trial will be recorded in the AE section of the eCRF. The ECG will be repeated if any results are considered to be clinically significant. A central ECG service will be used for reading all ECGs in order to standardize interpretations for the safety analysis.

ECG data including changes from baseline will be summarized through descriptive statistics by visit and treatment group. A shift table of the number and percentage of subjects who had normal and abnormal ECG findings will also be displayed by visit and treatment group.

The number and percentage of patients with notable QTcF interval prolongation, ie,

- >450 and \leq 480 msec,
- >480 and \leq 500 msec,
- >500 msec

and change from baseline into the intervals

- >30 and \leq 60 msec increase,
- >60 msec increase

will be displayed by treatment group, using the worst post-baseline value. Listings of ECG findings and a listing of ECG values will be provided.

9.6. Other Safety Data

C-SSRS Columbia-Suicide Severity Rating Scale (C-SSRS) will be collected at Screening, Baseline and Weeks 1, 3, 6, 12 and 14 and used to monitor suicidality.

This trial will use the “Baseline/Screening” and “Since Last Visit” versions of the scale. The “Baseline/Screening” version will be completed for all subjects at screening to determine eligibility whereas the “Since Last Visit” C-SSRS form will be completed at all visits after screening.

The C-SSRS is comprised of 10 categories with binary responses. The 10 categories include:

- Category 1 – Wish to be Dead
- Category 2 – Non-specific Active Suicidal Thoughts
- Category 3 – Active Suicidal Ideation with Any Methods (Not Plan) without Intent to Act
- Category 4 – Active Suicidal Ideation with Some Intent to Act, without Specific Plan
- Category 5 – Active Suicidal Ideation with Specific Plan and Intent
- Category 6 – Preparatory Acts or Behavior
- Category 7 – Aborted Attempt
- Category 8 – Interrupted Attempt
- Category 9 – Actual Attempt (non-fatal)
- Category 10 – Completed Suicide

Categories 1-5 represent Suicidal Ideation and categories 6-10 represent Suicidal Behavior. Each category is scored as 1 if there is a positive response in the category and a 0 otherwise. The Suicidal Ideation Score is the maximum suicidal ideation category that has a positive response and is 0 otherwise, that is, the Suicidal Ideation Score ranges from 0 to 5.

The maximum post-baseline result from the C-SSRS will be summarized for the FAS. The maximum of each subscale (suicidal ideation [Categories 1-5], suicidal behavior [Categories 6-10], suicidal ideation or behavior [Categories 1-10], and self-injurious behavior without suicidal intent) will be presented by treatment group. Note that the maximum is either 0 or 1. The number and percentage of patients with increased and decreased max post-baseline values of Suicidal Ideation Score compared to baseline values will be presented by treatment group. All C-SSRS elements will be reflected in a listing.

10. PHARMACOKINETICS

Single blood samples will be collected in appropriately labeled tubes for determination of the concentration of CVL-871 in plasma at Weeks 1, 3, 6, and 12.

Plasma concentration data of CVL-871 will be summarized for each dose at each time point using descriptive statistics and graphs based on all randomized subjects who received at least one dose of IMP and had at least one measurable CVL-871 concentration result. Additionally, all data will be listed for PK set. The descriptive statistics for PK concentrations will include geometric mean and geometric coefficient of variation (GCV) in addition to the descriptive statistics described in [Section 4.4.5](#).

The geometric mean and GCV will be calculated based on the mean and variance of the logarithmic transformed data with the following formula to transform back:

Geometric mean = $\exp(\text{mean})$, and

CV = $100 * \sqrt{\exp(\text{variance}) - 1}$.

11. PHARMACODYNAMICS

The planned timepoints for pharmacodynamic assessments are shown in the Schedule of Assessments (Table 4) which will be completed before the safety assessments and by the same identified caregiver.

All pharmacodynamic endpoints will be analyzed through descriptive statistical methods based on the mITT population. Pharmacodynamic endpoints with repeated post-baseline assessments will also be analyzed, using the mITT population, through statistical inference by using a mixed-model repeated measures (MMRM) analysis, including baseline score (if applicable), treatment, concomitant SSRI/SNRI use, visit (only measured at Visit 5 and 6), and the interaction between treatment group and visit as fixed factors in the model. Subject will be included as a random effect in the model.

An unstructured correlation matrix will be used to model the within-patient errors covariances. The Kenward-Roger approximation will be used to estimate the denominator of degrees of freedom. The least square (LS) mean of each treatment group, difference in the LS mean between the treatment groups, and the corresponding 80% and 95% CI of the differences and p-values will be provided.

If the MMRM model fails to achieve convergence due to complexity of model specification, different covariance structures will be used according to the following order till convergence is achieved:

1. Unstructured correlation (UN)
2. Heterogeneous Toeplitz (TOEPH)
3. Homogeneous Toeplitz (TOEP)
4. First-Order Autoregressive [AR(1)]
5. Compound Symmetry (CS)

The key research questions for the pharmacodynamic endpoints (ie, effect of CVL-871 treatment groups versus placebo) will be primarily addressed with a hypothetical strategy. As such, the missing values will be considered as missing at random (an MMRM analysis assumption).

The primary analysis for all PD endpoints will be performed as described above. However, if the number of subjects with evaluable baseline and post-baseline assessments for a specific PD endpoint is smaller than 15 (all treatment groups combined) or smaller than 2 in any treatment group, only descriptive statistical analyses will be conducted.

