4.4. Reporting Conventions

Statistical analysis will be performed using SAS® Version 9.4 or higher.

Standardized and validated SAS macros from PPD will be used to set-up table, listing, figure (TLF) formats (headers/footers and tabulation format) and to tabulate the summaries. All tables and listings will be independently validated using double programming; all figures will be independently validated manually.

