The instrument can be used as a stand-alone measure for specific neuropsychiatric domains (eg, dysphoria, apathy) or a combination of both (combination of domains with focus on one or more specific domains). Only the NPI-C apathy and dysphoria domains will be utilized as assessment measures in this trial and changes from Baseline to Weeks 6 and 12 will be analyzed through an MMRM for the mITT as described in Section 11. Other NPI-C domains will not be utilized. The NPI will be utilized to assess all 12 neuropsychiatric domains, including apathy and dysphoria, for confirmation of inclusion/exclusion criteria and for ongoing evaluation during the treatment phase.

Each NPI domain will be analyzed separately using an MMRM when sample size allows. In addition, all NPI and NPI-C data will be listed for the randomized patients with indicator for inclusion in the mITT analysis set.

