13.2. Impact of COMT (Val-Met) Status

Blood samples will be collected for analysis of catechol-O-methyltransferase (COMT) genotype. Sequencing was performed to detect the c.472G>A, p.Val158Met variant (Chr22:19951271) known familial variant ONLY. There will be one of three following results on the report,

- The variant of interest was NOT detected, corresponding to Val/Val
- The variant of interest was detected; heterozygous, corresponding to Met/Val
- The variant of interest was detected; homozygous, corresponding to Met/Met

The impact of COMT status on safety will be investigated by analysis of TEAEs, presented by primary SOC and PT, showing number and percentage of patients with at least 1 TEAE by COMT status (Met/Met vs Met/Val vs Val/Val) on the FAS.

To evaluate the impact of COMT status on pharmacodynamic, subgroup analyses will be conducted on the following pharmacodynamic endpoints based on the mITT set across the three COMT groups (Met/Met vs Met/Val vs Val/Val):

- NPI-C apathy domain score
- NPI apathy domain score
- DAIR score
- AES-C score

The subgroup analysis will be performed by subgroup rather than including an interaction term.

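### Does pairing a random subject effect with an unstructured two-visit covariance matrix in SAP 11 put the MMRM results at risk?

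*SAP*

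**What the plan says.** SAP section 11 describes one MMRM for all pharmacodynamic endpoints with repeated post-baseline assessments. Among the fixed factors it lists "visit (only measured at Visit 5 and 6", that is, Weeks 6 and 12. It then says "Subject will be included as a random effect in the model", and next "An unstructured correlation matrix will be used to model the within-patient errors covariances". Kenward-Roger degrees of freedom are specified.

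The fallback begins "If the MMRM model fails to achieve convergence due to complexity of model specification". It runs through unstructured (UN), heterogeneous Toeplitz (TOEPH), Toeplitz (TOEP), AR(1) and compound symmetry (CS). No step mentions the random effect.

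Protocol section 9.4.2 and the synopsis contain the same random-effect sentence but name no residual structure. Descriptive results are given regardless: "All pharmacodynamic endpoints will be analyzed through descriptive statistical methods based on the mITT population".

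**The concern.** A random intercept adds one constant to every element of a subject's covariance matrix. An unstructured 2 x 2 matrix can already take any admissible value, so the two components cannot be told apart. A statistician who reads the two sentences together sees an over-parameterised model.

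The worry is about the convergence rule. If the redundant term makes the Hessian singular, the software could report a failure that has nothing to do with the data. The fallback would then change the residual structure and keep the surplus term. If the step-down reached TOEP, AR(1) or CS, the two visits would be forced to share one variance, and the Week 12 standard error could be wrong.

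The reach is wide. There are up to 20 main fits: NPI-C 2, NPI 12 ("Each NPI domain will be analyzed separately using an MMRM when sample size allows"), DAIR 1, AES-C 1, mCGI-S 2 and CaGI-S 2. SAP section 14 adds up to 16 subgroup fits (2 endpoints x 8 subgroup levels). If the same model is used in SAP section 13.2, there are 12 COMT fits as well (4 endpoints x 3 genotypes).

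**Working it through.** The plan gives no figure on this point. Its nearest design figures, the detectable effects in SAP section 4.1, reproduce from a two-sample t calculation after 20% discontinuation: 25 x 0.8 = 20 per arm gives 0.6784 (stated 0.678), and 20 x 0.8 = 16 per arm gives 0.7608 (stated 0.761). That calculation uses no repeated-measures covariance, so this question does not touch it.

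**1. Identification.** Let s be the subject variance, J the 2 x 2 matrix of ones and R the residual matrix. The data inform only V = sJ + R, through V11, V12 and V22. The rank of the Jacobian of these three moments with respect to the covariance parameters is:

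| Structure | Parameters / rank with random subject | Parameters / rank without |
|---|---|---|
| UN | 4 / 3 | 3 / 3 |
| TOEPH | 4 / 3 | 3 / 3 |
| TOEP | 3 / 2 | 2 / 2 |
| AR(1) | 3 / 2 | 2 / 2 |
| CS | 3 / 2 | 2 / 2 |

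So the redundancy is real if the sentence is taken literally, and it amounts to exactly one parameter at every step.

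**2. Effect on the result.** Replace s by s + c and R by R - cJ. V is unchanged, so the likelihood, the least squares means and their standard errors are unchanged. Setting s = 0 recovers any unstructured V, so the best attainable fit is the same with or without the term.

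Check on one simulated data set with the SAP's fixed effects (assumed: 48 subjects, about 20% missing at Week 12). The fitted V has V11 = 6.106, V12 = 5.069 and V22 = 14.273. With s = 2, R is (4.106, 3.069, 12.273), and adding 2 to each element returns V. For s = 0, 1, 2, 3 and 4, -2 REML is 270.274615, the Week 12 difference is -1.31846 and its standard error is 1.40193 each time.

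**3. Kenward-Roger.** The score for s is the sum of the three UN scores, so the information matrix is singular. In the same data set the smallest Hessian eigenvalue is about 5e-08 with the term; without it the eigenvalues are 0.155, 0.867 and 3.663. A generalised inverse carries the same information about V, and the Kenward-Roger standard error computed that way is identical with and without the term.

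**4. Does the fallback lead elsewhere?** To land on TOEP, AR(1) or CS because of singularity, UN and TOEPH must fail while a structure with the same rank deficiency of one passes. The table gives no reason for that. If singularity alone stops a fit, it stops all five; if it does not, UN is accepted. TOEPH at two visits is UN in another parameterisation, so stopping there changes nothing.

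**5. Size of the equal-variance error.** With complete data and a Week 12/Week 6 variance ratio r, the Week 12 standard error is multiplied by sqrt((1 + r)/(2r)). For r = 1.5 this is sqrt(2.5/3) = 0.913, 9% too small. Over assumed ratios from 1.2 to 2.0 it is 4% to 13% too small; over the inverse ratios it is 5% to 22% too large. The documents give no ratio. These errors belong to equal-variance structures in general and arise equally without a random effect.

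**The case for a change.** The best case for acting is that the SAP lets convergence choose the reported model, so the specification should not contain a built-in reason for a convergence check to fail. Samples may be small: section 11 permits inference from 15 subjects overall and section 14 permits subgroup models from 9, so genuine failures are plausible and should be distinguishable from artificial ones. Two independent programmers might also code the sentence differently. The edit would cost one sentence in section 11 and one line in section 15.

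The redundancy stands. So does the uncertainty about software: section 4.4 says "Statistical analysis will be performed using SAS", and SAS was not run.

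The harm is not shown. A singular Hessian is not the same as non-convergence. In separate code, a Newton REML fit of UN plus random subject converged in all 100 simulated data sets (5 and 8 per arm) to the same REML value as UN alone. A bounded optimiser reported convergence in 354 of 360 data sets (5, 8 and 20 per arm). A few of its small-sample fits reached a different likelihood, but failures of UN alone were not counted, so those runs cannot be charged to the random effect.

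On double programming, an accepted fit under either reading gives the same difference and standard error. Section 15 lists departures from the protocol, and here the SAP repeats the protocol, so its silence is not an omission.

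**Conclusion.** The concern is right about the algebra but does not call for a change. As worded, section 11 has one covariance parameter too many at two visits. It is best treated as loose wording inherited from the protocol: in an MMRM whose within-patient covariance is assigned to the residual matrix, the subject has to be named as the repeated-measures unit, and the sentence may do no more than that. The model code is not in the documents, so the intended reading cannot be proved.

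Neither reading changes a result. An accepted unstructured fit has the same treatment difference and standard error with or without the term, and no route from the redundancy to an equal-variance structure has been demonstrated. If software did reject the literal model at every step, the term an analyst would drop is the one that carries no information. The endpoints concerned are secondary or exploratory and are summarised descriptively in any case. The conclusion rests on two post-baseline visits and a positive definite fitted covariance matrix; it makes no claim about how often SAS would issue a warning.
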